Clinical Intervention Study Protocol

FULL PROTOCOL TITLE

Effect of a Modified Oxygen Mask Associated to Nasal Prongs During High Flow Oxygenation in ICU patient: a cross over study

Principal Investigator:

[name], Msc, Epicura Hornu, Condorcet Tournai

STUDY TEAM ROSTER

[name] NT Msc ICU Hospital TIVOLI [name] ICU Hospital TIVOLI [name]

[contact]

[name] PT Msc Hospital Epicura Hornu [name]
[contact]

[name] PT Msc Condorcet Laboratory Tourna Belgium [name]
[contact]

[name] PT PhD IREC, Cliniques Universitaires Saint Luc Bruxelles [name] [contact]

[name] MD (Head chief of ICU) Hospital Epicura Hornu [name] and ICU Hospital TIVOLI [name]
[contact]

PARTICIPATING STUDY SITES

Hospital Epicura Hornu [name]

Hospital Tivoli [name]

PRÉCIS

Study Title

Effect of a Modified Oxygen Mask Associated to Nasal Prongs During High Flow Oxygenation in ICU patient: a cross over study

[figure not shown]
Objectives

The primary endpoint was the change of PaO2.

The secondary endpoint was the change of PaCO2, pH and patient respiratory comfort

Design and Outcomes

This is a single-center, randomized, blind investigator, 2-way crossover study design to test the efficacy of a special mask (DTM) add above nasal prongs during High Flow Oxygenation

**Figure 1**

Interventions and Duration

Sequence (Figure 1): The patient should be placed in semi-seated (position at 45 °)

Patient will be oxygenated with high-flow nasal cannula (HFNC). Fraction delivered in Oxygen and flow rate will be adjusted to obtain a Saturation in oxygen > at 90%.

1. Arterial gazometry will be taken after 20 and 60 minutes with HFNC.
2. The clinician will associate the Double Trunk Mask (DTM) with the same parameters of the high-flow nasal cannula. Arterial gazometry will be performed after 20 and 60 minutes after placement of DTM.
3. After the withdrawal of DTM, arterial gazometry will be performed after 20 and 60 minutes

Sample Size and Population

Enrolled participants had severe hypoxia being treated at Intensive Care Unit

1. STUDY OBJECTIVES

1.1 Primary Objective

The experimental treatment will result of an increase of PaO2 when the special mask will be adding above nasal prongs compared with no mask addition.

1.2 Secondary Objectives

The Secondary objectives is the change of PaCO2, pH and patient respiratory comfort with the mask addition above prongs

2. BACKGROUND AND RATIONALE

2.1 Background on Condition, Disease, or Other Primary Study Focus

Oxygen therapy is the main treatment during Hypoxia. In this case, arterial Pressure Oxygenation should be maintained within strict limits. High Flow Oxygenation system can be used to administer Oxygen therapy (FDO2). In this case, high inspiratory flow decreases fraction delivered in oxygen. The addition of a special mask (Double Trunk Mask) can limits the fraction delivered in oxygen decrease.

2.2 Study Rationale

Few studies emphasize the decreases of FDO2 during inspiratory flow increases.

Studies:

Duprez F. Effet du pattern respiratoire sur la FiO2 au cours de l'oxygénothérapie Revue des Maladies Respiratoires. Volume 32, Supplement, January 2015, Page A81

The intervention has been chosen because in our experience, double trunk mask is currently used to fight FDO2 decrease during inspiratory flow increase.

3. STUDY DESIGN

This is a single-center, randomized, blind investigator, 2-way crossover study design. Enrolled participants had severe hypoxia being treated at Intensive Care Unit associated with a hospital in Hornu (Epicura) and hospital Tivoli.

The study consisted of two intervention periods separated by a washout period of 20 minutes. (Figure 1)

The objective of the study is to determine whether adjunctive mask of our design (Double Trunk Mask - DTM) has an effect on increasing arterial pressure in Oxygen (PaO2) diagnosed with severe hypoxia (See figure 1).

The protocol and informed consent documents were reviewed and approved by a recognized ethics review board at the study facility. The study was performed in accordance with the Declaration of Helsinki.

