4.2 Exclusion Criteria

- *Hypercapnia (> 45 mm Hg with respiratory acidosis)*
- *Cardiogenic pulmonary edema*
- *COPD*
- *Pulmonary fibrosis*
- *Hypoventilation obesity syndrome*
- *Arterial pressure < 60 mm Hg or treatment by epinephrine > to 0,1 gamma/kg/minute*
- *Deterioration of awareness (Glasgow scale < or = 12)*
- *Acute confusional state.*

Participants were randomized in a 1:1 ratio to receive either (CHFONP) classical High Flow Oxygenation with nasal prongs (20 minutes) or CHFNOP with an adjunctive of a DTM.

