5. STUDY INTERVENTIONS

Interventions, Administration, and Duration

Sequence (Figure 1): The patient should be placed in semi-seated (position at 45 °) Patient will be oxygenated with high-flow nasal cannula (HFNC). Fraction delivered in Oxygen and flow rate will be adjusted to obtain a Saturation in oxygen > at 90%.

- 1. Arterial gazometry will be taken after 20 and 60 minutes with HFNC.*
- 2. The clinician will associate the Double Trunk Mask (DTM) with the same parameters of the high-flow nasal cannula. Arterial gazometry will be performed after 20 and 60 minutes after placement of DTM.*
- 3. After the withdrawal of DTM, arterial gazometry will be performed after 20 and 60 minutes*

Consenting Procedure

The protocol and informed consent documents were reviewed and approved by a recognized ethics review board at the study facility. The study was performed in accordance with the Declaration of Helsinki.

Enrollment, Baseline, and/or Randomization

Enrollment

Enrolled participants had severe hypoxia being treated at Intensive Care Unit associated with a hospital in Hornu (Epicura).and Tivoli Hospital.

Baseline Assessments

For participants who have successfully been screened for eligibility and are enrolled into the study, baseline assessments are performed against which to measure the study outcome:

Age, Weight, Height, arterial pressure (S/D/M), Cardiac frequency, respiratory frequency, PaO₂, PaCO₂, pH, MRC dyspnea, MRC Comfort, Glasgow Coma Scale.

Blinding

Data's should be evaluated in blind by an independent assessor

Adverse Event Assessment

Safety was assessed by the number of participants with adverse events (AEs). AEs were collected by systematic assessment using terms from the Medical Dictionary for Regulatory Activities (MedDRA), version 11.1 in participants who received one or more doses of intervention. Adverse events during washout were not collected.

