6. STATISTICAL CONSIDERATIONS

9.1 General Design Issues

Cross over design is the most appropriate to compare one intervention in the same groups of persons

Length of washout chosen is 30 to 60 minutes because after this period, following parameters are stabilized after intervention (PaO₂, PaCO₂, pH)

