9.2 Outcomes

Discuss how the outcomes will be analyzed. Describe whether the documentation of an outcome will be reviewed and adjudicated by a committee, how quickly the committee will perform the adjudication, and whether the committee will be masked

to the participant's intervention group assignment.

Primary Outcome

PaO₂ is the primary outcomes observed. PaO₂ is the principal parameters observed

Secondary Outcomes

PaCO₂, pH, MRC dyspnea and comfort

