9.3 Data Analyses

All participants who received this intervention and completed two phases of study were included in the efficacy analysis.

A sample size of 15 participants was needed to provide 90% power to detect a 10 mm Hg difference in PaO₂. ANOVA for repeated measures followed by a post hoc test were used to compare the difference between participants receiving (high-flow nasal cannula + DTM) and with high-flow nasal cannula alone.

The test was performed with a significance level of 0.05 (two-sided). Statistical analyses were carried out using SigmaPlot software version 11.0 (Systat Software Inc. UK).

Note: In accordance with NIH policy, if data from prior studies do not negate strongly the existence of significant differences of clinical or public health importance in the intervention effect between gender and racial/ethnic subgroups, a statement should be included noting that a valid analysis of the intervention effect will be performed in these subgroups. If data from prior studies do not strongly support the existence of significant differences in the intervention effect between subgroups, then the analyses need not have high statistical power for detecting clinically meaningful differences.

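### The washout is 20 minutes in Section 3 but 30 to 60 minutes in Section 6, the 20-minute HFNC period in 4.2 cannot hold the 60-minute gas, and the primary PaO2 has no sampling time

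*Combined protocol and SAP*

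**What the plan says.** **Washout.** Section 3 (Study Design): "The study consisted of two intervention periods separated by a washout period of 20 minutes". Section 6, under 9.1 (General Design Issues): "Length of washout chosen is 30 to 60 minutes because after this period, following parameters are stabilized after intervention", with PaO2, PaCO2 and pH named as the parameters.

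**Period length.** The randomisation sentence at the end of 4.2 describes one arm as "classical High Flow Oxygenation with nasal prongs (20 minutes" (the parenthesis closes there). It gives no duration for the mask (DTM) arm.

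**Sampling.** Section 5, step 1: "Arterial gazometry will be taken after 20 and 60 minutes with HFNC". Step 2 sets the same two times after the mask is placed. Step 3: "After the withdrawal of DTM, arterial gazometry will be performed after 20 and 60 minutes". The Précis repeats these steps.

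**Primary outcome.** The Précis says "The primary endpoint was the change of PaO2" and 9.2 says "PaO₂ is the primary outcomes observed". The analysis in 9.3 reads "ANOVA for repeated measures followed by a post hoc test were used to compare the difference between participants receiving" HFNC with the mask and HFNC alone. The objective in 1.1, the 10 mm Hg power statement and the ANOVA all leave the sampling time open.

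**Design.** Sections 3 and 4.2 describe a randomised two-period crossover with a washout. Section 5 and the Précis describe a fixed order of HFNC, mask, HFNC, with no separate washout.

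**The concern.** The only statement in the plan about how fast blood gases settle is the one in 9.1, and it concerns settling after an intervention. Against that statement, a 20-minute washout is too short, and a gas drawn 20 minutes after the mask comes off is too early to count as a clean HFNC value. If such a gas serves as the comparator, any leftover mask effect raises the HFNC value and shrinks the difference the trial is meant to detect.

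The missing sampling time makes this worse. Each phase has two candidate PaO2 values and no rule for choosing or combining them, so the choice could be made after the data are seen. The text also gives sites two washout lengths, and an HFNC period that ends 40 minutes before its own last gas.

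**Working it through.** **Inputs from the documents.** Washout 20 minutes (Section 3) or 30 to 60 minutes (9.1); HFNC period 20 minutes (4.2); gases at 20 and 60 minutes in each phase (Section 5); target difference 10 mm Hg and two-sided 0.05 (9.3). The plan's calculated figure, 15 patients, cannot be reproduced because no standard deviation is given. It is not disputed here, and 10 mm Hg serves only as a scale.

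**1. Direct conflicts.** 30 − 20 = 10 and 60 − 20 = 40, so the Section 3 washout is 10 to 40 minutes shorter than the 9.1 figure and the two do not overlap. A 60-minute gas falls 60 − 20 = 40 minutes after a 20-minute period has ended.

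**2. Minutes since mask removal at each HFNC gas that follows the mask.** This is washout *w* plus sampling time *s*, with the mask assumed off during washout.

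| Reading | *s* = 20 | *s* = 60 |
|---|---|---|
| Section 5 sequence (*w* = 0) | 20 | 60 |
| Two-period, *w* = 20 | 40 | 80 |
| Two-period, *w* = 30 | 50 | 90 |

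Only the Section 5 gas at 20 minutes comes before the 30 to 60 minute window opens. Those at 40 and 50 minutes lie inside it. Every 60-minute gas is at or beyond its end.

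**3. Illustration of size (all assumed).** Suppose the mask acts at once, its true effect is *D* = 10 mm Hg, and after removal the remaining fraction is *r*(*t*) = (1 − *c*)^(*t*/*T*), where a share *c* is gone by *T* minutes. Considering carryover alone, the expected differences are:

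- mask minus return HFNC: *D*(1 − *r*(*t*));
- mask minus the mean of both HFNC phases: *D*(1 − *r*(*t*)/2);
- randomised two-period: *D*(1 − *r*(*w* + *s*)/2), since only half the patients have the mask first.

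Example: *c* = 0.95, *T* = 60, *t* = 20 gives *r* = 0.05^(1/3) = 0.368 and 10 × (1 − 0.368) = 6.3.

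| Contrast (mm Hg) | 99% gone at 30 min | 95% at 30 | 95% at 60 | 90% at 60 |
|---|---|---|---|---|
| Return HFNC, 20 min | 9.5 | 8.6 | 6.3 | 5.4 |
| Mean of both HFNC, 20 min | 9.8 | 9.3 | 8.2 | 7.7 |
| Two-period, *w* = 20, 20 min | 10.0 | 9.9 | 9.3 | 8.9 |
| Return HFNC, 60 min | 10.0 | 10.0 | 9.5 | 9.0 |
| Mean of both HFNC, 60 min | 10.0 | 10.0 | 9.8 | 9.5 |
| Two-period, *w* = 20, 60 min | 10.0 | 10.0 | 9.9 | 9.8 |

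**4. Time drift in the fixed sequence.** Assume 60-minute phases back to back and PaO2 drifting by *b* per minute. The 60-minute gases then fall at 60, 120 and 180 minutes. Mask minus first HFNC contains +60*b*, and mask minus return HFNC contains −60*b*. The mean of the two HFNC gases is centred at (60 + 180)/2 = 120, so linear drift cancels. If a separate washout *w* precedes the return phase, the centre moves to 120 + *w*/2, and −*bw*/2 remains.

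**5. Two candidate times.** If both were tested at 0.05 and either could be claimed, the type I error would be 1 − 0.95² = 0.0975 under independence, and less with positive correlation. The plan does not say that it would do this.

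**The case against.** The strongest reply is that the headline conflict matters little in the design named in Section 3. After a 20-minute washout the first HFNC gas is 40 minutes after removal, inside the 9.1 window, and the illustration loses less than 1 mm Hg in the 95% cases and about 1.1 in the slowest. The larger losses arise only in the Section 5 sequence, which has no separate washout, so correcting the Section 3 figure would not change them. This stands, and it is why the primary sampling time and the comparator matter more than the washout number.

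The decay model is assumed, not documented. This also stands: the table shows what could happen and estimates nothing.

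The 20 minutes in 4.2 may be an editorial slip, since Section 5 and the Précis agree on 20 and 60 minutes. That is plausible, but the text still needs correcting.

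Figure 1 is not shown in this copy and may give a timeline. It could agree with at most one washout length and one HFNC duration, so the conflicts in the text would remain. It might, however, tell sites which timing applies.

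A repeated-measures ANOVA could use both times. Section 9.3 does not say that it does, nor how the two would be combined.

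**Conclusion.** The point holds as an internal contradiction on washout and period length together with an incompletely defined primary outcome. The demonstrable risk is confined to one use of the data: the gas 20 minutes after mask withdrawal in the Section 5 sequence, taken as the HFNC value. Such a comparison may understate the mask effect. Under the assumptions shown, a true 10 mm Hg would appear as 5.4 to 9.5 at 20 minutes and 9.0 to 10.0 at 60 minutes. The actual size of any bias cannot be determined from the documents.

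A reader might infer more, in four ways that the documents do not support:

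- **That a 20-minute washout materially biases the randomised crossover.** The 40-minute timing argues against this.
- **That comparing the mask with the first HFNC phase is free of bias.** It is free of mask carryover only; in a fixed order it is fully confounded with time.
- **That the mask acts slowly, or that the two sampling times are pooled.** The plan states neither.
- **That the illustration shows which washout between 30 and 60 minutes suffices.** It cannot, because its settling rates are assumed.

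**What to change.** 1. In 9.2 and 9.3, make the already scheduled 60-minute PaO2 of each phase the primary value and the 20-minute value secondary.
2. Correct the Section 3 washout to one figure from 30 to 60 minutes, and say whether it is separate from the return-to-HFNC phase.
3. Make the period in 4.2 at least 60 minutes, for both arms, to match Section 5.
4. State whether the trial is the randomised two-period crossover or the HFNC–mask–HFNC sequence. If the sequence is kept, name the comparator: first HFNC, return HFNC or their mean. The mean also balances linear drift when the phases are equally spaced.

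**Cost.** No extra gases are needed. A patient who stops between 20 and 60 minutes has no primary value for that phase. With 15 patients and an efficacy analysis limited to those who complete two phases (9.3), each such loss is 1/15, or 6.7%, of the sample, so report their number and their 20-minute values. A separate washout would be 10 to 40 minutes longer per patient than Section 3 states. Section 5 collects no adverse events during washout, so that unobserved time grows with it.

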4. SELECTION AND ENROLLMENT OF PARTICIPANTS

4.1 Inclusion Criteria

- *At least 18 years of age*
- *Diagnosed with severe Hypoxia (PaO₂/FiO₂ < 300 mm Hg)*
- *Dyspnea with severe rest at stake accessory muscles of respiration*
- *Respiratory rate (RR) ≥ 25 CPM*
- *PaCO₂ ≤ 45 mmHg, patient with an arterial catheter and without hemodynamic instability*
- *Glasgow Coma Scale ≥ 12/15*
- *Written consent.*
- *Participants were also required to have a sufficient level of education to understand study procedures and be able to communicate with site personnel.*

4.2 Exclusion Criteria

- *Hypercapnia (> 45 mm Hg with respiratory acidosis)*
- *Cardiogenic pulmonary edema*
- *COPD*
- *Pulmonary fibrosis*
- *Hypoventilation obesity syndrome*
- *Arterial pressure < 60 mm Hg or treatment by epinephrine > to 0,1 gamma/kg/minute*
- *Deterioration of awareness (Glasgow scale < or = 12)*
- *Acute confusional state.*

Participants were randomized in a 1:1 ratio to receive either (CHFONP) classical High Flow Oxygenation with nasal prongs (20 minutes) or CHFNOP with an adjunctive of a DTM.

4.3 Study Enrollment Procedures

Enrolled participants had severe hypoxia being treated at Intensive Care Unit associated with a hospital in Hornu (Epicura).and Tivoli Hospital.

5. STUDY INTERVENTIONS

Interventions, Administration, and Duration

Sequence (Figure 1): The patient should be placed in semi-seated (position at 45 °) Patient will be oxygenated with high-flow nasal cannula (HFNC). Fraction delivered in Oxygen and flow rate will be adjusted to obtain a Saturation in oxygen > at 90%.

- 1. Arterial gazometry will be taken after 20 and 60 minutes with HFNC.*
- 2. The clinician will associate the Double Trunk Mask (DTM) with the same parameters of the high-flow nasal cannula. Arterial gazometry will be performed after 20 and 60 minutes after placement of DTM.*
- 3. After the withdrawal of DTM, arterial gazometry will be performed after 20 and 60 minutes*

Consenting Procedure

The protocol and informed consent documents were reviewed and approved by a recognized ethics review board at the study facility. The study was performed in accordance with the Declaration of Helsinki.

Enrollment, Baseline, and/or Randomization

Enrollment

Enrolled participants had severe hypoxia being treated at Intensive Care Unit associated with a hospital in Hornu (Epicura).and Tivoli Hospital.

Baseline Assessments

For participants who have successfully been screened for eligibility and are enrolled into the study, baseline assessments are performed against which to measure the study outcome:

Age, Weight, Height, arterial pressure (S/D/M), Cardiac frequency, respiratory frequency, PaO₂, PaCO₂, pH, MRC dyspnea, MRC Comfort, Glasgow Coma Scale.

Blinding

Data's should be evaluated in blind by an independent assessor

Adverse Event Assessment

Safety was assessed by the number of participants with adverse events (AEs). AEs were collected by systematic assessment using terms from the Medical Dictionary for Regulatory Activities (MedDRA), version 11.1 in participants who received one or more doses of intervention. Adverse events during washout were not collected.

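### The plan declares a 1:1 randomised two-period crossover, but its only written procedure is one HFNC, DTM, HFNC order; if followed, DTM versus first HFNC is confounded with time

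*Combined protocol and SAP*

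**What the plan says.** Three places declare a randomised crossover.

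- The Précis (Design and Outcomes) and Section 3 both state: "This is a single-center, randomized, blind investigator, 2-way crossover study design".
- Section 3 adds: "The study consisted of two intervention periods separated by a washout period of 20 minutes".
- The last paragraph of Section 4.2 states: "Participants were randomized in a 1:1 ratio to receive either (CHFONP) classical High Flow Oxygenation with nasal prongs (20 minutes", and gives HFNC plus the mask as the alternative.

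The procedure is written out twice, in the Précis (Interventions and Duration) and in Section 5, in the same three steps:

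1. Settings are adjusted on HFNC to a saturation target, and blood gases are taken at 20 and 60 minutes.
2. "The clinician will associate the Double Trunk Mask (DTM) with the same parameters of the high-flow nasal cannula", with gases again at 20 and 60 minutes.
3. "After the withdrawal of DTM, arterial gazometry will be performed after 20 and 60 minutes".

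Both versions cite Figure 1 for the sequence. The figure is not shown in the text available for this review.

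On analysis, Section 9.3 says "ANOVA for repeated measures followed by a post hoc test were used to compare the difference between participants receiving" HFNC with the mask and HFNC alone. It restricts the efficacy set to patients who completed two phases. It does not say which HFNC phase is the comparator and names no period or sequence term.

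**The concern.** A two-period crossover is protected from time trends because some patients receive the treatments in one order and the rest in the other. The written steps offer one order only. In Section 5, the heading that mentions randomisation is followed by enrolment and baseline text but no randomisation procedure. Nor can the steps simply be read in reverse: step 2 carries over settings already fixed on HFNC, and step 3 is a withdrawal.

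The primary objective (Section 1.1) is a higher PaO2 with the mask than without it. Section 4.1 requires PaO2/FiO2 below 300 mm Hg and a respiratory rate of at least 25, and each step is sampled out to 60 minutes. Nothing in the documents supports assuming that PaO2 would stay constant across the phases without the mask. A rise would be credited to the mask and a fall would hide its effect. A non-randomised A-B-A comparison could then be reported as a randomised crossover.

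**Working it through.** **1. What each contrast estimates.** Let m1, m2 and m3 be the mean PaO2 that patients would have in the three phases without the mask, and let τ be the mask effect.

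- Fixed order, DTM minus first HFNC: τ + (m2 − m1). The drift enters one for one.
- Fixed order, DTM minus the mean of both HFNC phases: τ + m2 − (m1 + m3)/2. The extra term is zero when drift is linear. It is not zero otherwise: a rise of 5 mm Hg followed by a plateau leaves 5 − (0 + 5)/2 = 2.5 mm Hg. Any mask effect that persists into phase 3 also biases this contrast.
- Two randomised orders, with drift δ between periods and no carry-over: the mean difference is τ + δ in HFNC-first patients and τ − δ in mask-first patients. Their average is τ.

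**2. The plan's own figure.** Section 9.3 gives n = 15, 90% power, 10 mm Hg and two-sided 0.05, but no SD. The sample size can therefore only be solved backwards. With a paired t-test (my assumption; the plan names a repeated-measures ANOVA), df = 14 and critical value 2.145, power is 90% when the noncentrality 10/(SD/√15) equals 3.489. This gives SD = 10 × 3.873/3.489 = 11.1 mm Hg. SDs of differences from about 10.7 to 11.1 all lead to n = 15.

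**3. False positives under the fixed order.** Set τ = 0. The noncentrality is drift/(11.1/√15) = drift/2.866. The documents give no drift, so a range is shown.

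| Drift, phase 1 to 2 (mm Hg) | Noncentrality | P(significant) |
|---|---|---|
| 0 | 0 | 5% |
| 1 | 0.35 | 6% |
| 2 | 0.70 | 10% |
| 3 | 1.05 | 16% |
| 5 | 1.74 | 37% |
| 8 | 2.79 | 74% |
| 10 | 3.49 | 90% |

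At a drift of 5 mm Hg, the 37% becomes 61.5% if the SD is 8 and 22.5% if it is 15. The bias in mm Hg equals the drift and needs no SD.

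**4. Two randomised orders at n = 15.** Split 8:7 with a period term, df = 13 and SE = (SD/2) × √(1/8 + 1/7). With no carry-over, power for 10 mm Hg is 91.5% at SD 10.7, 90.0% at SD 11.0 and 89.5% at SD 11.1. In simulation (40,000 trials, SD 11.1), the false-positive rate stayed at about 5% for drifts of 0, 2, 5 and 10 mm Hg. At SD 15, power is 66%, but the paired t-test also has only 67% there. That loss comes from the SD, not from randomising the order.

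**The case against.** The strongest reply is that the sequence is meant to be read from Figure 1. Both versions of the steps cite it, and so does Section 3. If it shows two orders, the steps may describe one arm only, and sites would also have the 1:1 statement. This stands, and it limits the point. A reader might infer that patients were not randomised, or that sites would give everyone the same order. The documents support neither. With a two-order figure, the written steps would be incomplete and in conflict with it, and would still need correcting.

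A second reply is that the return to HFNC in step 3 supplies a control for drift. It can, but only for linear drift, only without carry-over and only if the analysis uses it. The ANOVA in Section 9.3 could include that phase, but the text does not say so. An efficacy set defined by two phases, set against three steps, leaves it unclear.

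A third reply is that the error rates depend on an invented drift. That is correct: they run from 6% to 90% over 1 to 10 mm Hg, and no single value should be quoted as the expected one. The identity in step 1 of the working does not depend on them.

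Section 9.1 says that PaO2, PaCO2 and pH stabilise after the washout. That bears on carry-over of the mask effect, not on change in the patient's underlying condition.

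**Conclusion.** The contradiction is certain as far as the text goes and must be fixed, because whether the order is randomised decides both the valid analysis and the honest label. The confounding is conditional on the steps being followed as written, and it concerns DTM against first HFNC. There the bias equals whatever PaO2 change occurs between phases 1 and 2. The false-positive rates are illustrations that rest on a paired t-test, an SD of about 11.1 mm Hg solved back from n = 15, and assumed drifts.

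A reader might also infer that randomising the order costs patients, since power falls just below 90% at SD 11.1. That is an artefact of solving the SD to give exactly 90% with one more degree of freedom; at SD 10.7 to 11.0, 15 patients still suffice. The documents give no basis for putting a size on carry-over, so no power figure is offered for it.

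**What to change.** Bring the Précis, Sections 3, 4.2, 5 and 9.3 and Figure 1 to one design.

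**(a) If the order is randomised.** Write the steps as two allocated sequences and say how allocation is applied. State the role of the third phase. The sponsor must also reconcile the wording on unchanged settings in step 2 with a mask-first order. Put period and sequence in the primary model. The cost is an allocation list and rewritten steps. Under the implied SD of 10.7 to 11.1, power at n = 15 stays at about 90%, so essentially no more patients are needed, provided that there is no carry-over. This route is not open for patients already treated in a fixed order; Sections 3, 4.2 and 9.3 are partly in the past tense.

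**(b) If the fixed order is or was run.** Remove the terms randomized, 1:1 and 2-way crossover, and call the study a non-randomised A-B-A comparison. Name the comparator phase in Section 9.3. One suitable contrast is DTM minus the mean of the two HFNC phases, with DTM against each HFNC phase beside it. State that it cancels linear drift only and assumes no carry-over. Specify it before the data are seen, or label it post hoc. The changes are to text only, but the randomised claim is given up.

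**Separate items to reconcile, which do not follow from the missing sequence.** Section 3 gives a 20-minute washout, while Section 9.1 says "Length of washout chosen is 30 to 60 minutes because after this period, following parameters are stabilized after intervention". Section 4.2 gives 20 minutes of HFNC, while the Précis and Section 5 sample it to 60 minutes.

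### Adverse events in washout are excluded by rule from the only safety count, and no section says when AE collection ends

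*Combined protocol and SAP*

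**What the plan says.** Section 5, under Adverse Event Assessment, is the only place where AEs are mentioned. It measures safety by counting participants who had an AE, assesses AEs systematically with MedDRA terms "in participants who received one or more doses of intervention", and closes with the rule "Adverse events during washout were not collected". It gives no start, end or follow-up time for collection.

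Four other statements bear on what that rule removes:

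- Section 3: "The study consisted of two intervention periods separated by a washout period of 20 minutes".
- Section 9.1: "Length of washout chosen is 30 to 60 minutes because after this period, following parameters are stabilized after intervention" (PaO2, PaCO2 and pH).
- The sequence in the Précis, repeated in section 5, runs HFNC, then DTM added, then DTM removed. Its third step reads: "After the withdrawal of DTM, arterial gazometry will be performed after 20 and 60 minutes". It does not call that step washout or a study period.
- Section 9.3: "All participants who received this intervention and completed two phases of study were included in the efficacy analysis".

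**The concern.** This is a stated exclusion, not a gap left by silence. It applies to an interval that the plan itself treats as unsettled: section 9.1 justifies the washout by saying that the blood gas values are stable once it is over, which implies that they may still be moving while it lasts. The participants are intensive care patients with PaO2/FiO2 below 300 mm Hg and a respiratory rate of at least 25. An event that starts soon after a condition is withdrawn is one that a safety count should be able to show.

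At stake is the completeness of the safety report. Following the rule can omit events but can never add one, so any error in the count is in one direction.

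**Working it through.** The plan states no figure for AE collection, so there is nothing to reproduce. The check sets the sections side by side.

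**1. Is collection restored elsewhere?** No. The objectives (1.1, 1.2), the outcomes (9.2), the analysis (9.3) and data collection (10.1) do not mention AEs. No section gives an end to collection.

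**2. What does the rule do to the count?** Someone who has received a condition and whose only AE starts in washout belongs to the AE population of section 5 but has no recorded event. Each such participant lowers the count by 1. Section 9.3 plans 15 participants; taking 15 as the denominator, 1/15 = 6.7 percentage points.

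**3. How long is the window?** 20 minutes by section 3 and 30 to 60 minutes by section 9.1; 60/20 = 3, a threefold range. As an illustration only, let the uncollected share of observed time be w / (2p + w), with washout w and two periods of length p. The blood gas schedule suggests p = 60; the randomisation paragraph at the end of section 4.2 gives 20 minutes for HFNC alone.

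| Period p (min) | w = 20 | w = 30 | w = 60 |
|---|---|---|---|
| 60 | 20/140 = 14% | 30/150 = 20% | 60/180 = 33% |
| 20 | 20/60 = 33% | 30/70 = 43% | 60/100 = 60% |

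These are shares of time, not of events.

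**4. Where is the window?** The text allows three readings, with different consequences.

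- *Washout between the two periods (section 3).* A participant who stops there because of an event has not completed two phases, so section 9.3 drops that person from the efficacy set while section 5 leaves the event uncounted. Neither analysis then shows it. A late mask effect or a withdrawal event can arise in this washout only in those given DTM first. With 1:1 allocation to order, that is 15/2 = 7.5, so 7 or 8 participants.
- *Washout is step 3, after DTM withdrawal.* The participant has already had HFNC and DTM and may count as having completed two phases, so may stay in the efficacy set. AEs after mask removal go uncounted.
- *Step 3 is a study period and there is no separate washout.* The window is 0 minutes and the exclusion has little or no reach. The missing end of collection remains.

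Figure 1 is not reproduced in the text available for this review and may settle which reading applies.

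**The case against.** The strongest reply is that the consequence may be small or nil. Safety is neither an objective nor a listed outcome. The written sequence has no washout between HFNC and DTM, and if step 3 is a study period the rule may exclude nothing. Blood gases at 20 and 60 minutes after DTM withdrawal would record some physiological change in any case. The 20-to-60-minute range mostly restates a separate inconsistency about washout length.

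Much of this stands as a limit on size. It does not remove the point. Section 3 says that a washout exists, section 5 writes an exclusion for it, and the end of collection is missing on every reading. Blood gases serve the PaO2, PaCO2 and pH outcomes and do not replace AE collection.

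The reply also defeats two stronger readings. A reader might infer that anyone who stops in washout because of an event vanishes from both the safety count and the efficacy analysis. That follows only if washout lies between the two phases. If washout is step 3, such a participant may still be a completer, and section 9.3 does not define a phase. A reader might also infer that late mask effects are missed in every participant. In a between-period washout, those given HFNC first have not yet worn the mask.

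**Conclusion.** The point holds in a limited form and is worth correcting. By stated rule, the only safety measure omits AEs that start in washout, and collection has no stated end. The count is too low by 1 for each participant whose only AE starts in that window. The window is 20 to 60 minutes by the plan's own figures, or 0 minutes if step 3 is a study period with no separate washout.

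This rests on two assumptions: that either condition counts as an intervention for the AE population, and that the 15 planned participants are the denominator when one missed participant is put at 6.7 percentage points. The documents give no AE rate, so the number of missed events cannot be derived, and nothing here shows that any event was missed. Nor does the AE rule affect the PaO2 result. Confidence is high in the omission and lower in its reach, which depends on where washout sits.

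**What to change.** Replace the exclusion with: 'Adverse events are collected continuously from the start of the first period, through washout, until the end of a fixed observation interval after the final condition, the same for both orders; events starting in a period are tabulated under that condition, and events starting in washout are tabulated separately under the immediately preceding condition.' An interval common to both orders covers the time after mask removal when DTM comes last. The separate tabulation settles attribution in washout.

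Reconcile sections 3, 5 and 9.1 on whether step 3 is washout and how long washout lasts, so that the window is defined. The sponsor must choose the lengths; this point does not depend on which is chosen.

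The AE paragraph is in the past tense while the sequence is in the future tense, so the stage of conduct is unclear. If conduct is complete, state in the report that washout AEs were not collected and that the AE count is a lower bound.

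The cost is a protocol sentence, a CRF line and a possibly higher AE count. If conduct is complete, it is one limitation statement.
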